### OEND Best Practice Recommendations

Study staff disseminated best practice recommendations to all SSPs enrolled in the trial. Details of OEND best practice recommendations can be found elsewhere [43]. Briefly, a Delphi study was carried out to develop a set of best practices for OEND implementation within SSPs. Experts for the Delphi study included people in paid and volunteer leadership and direct service positions in SSPs, OEND researchers, people who work in state or local health departments, and people who use drugs who deliver and access SSP/OEND services. All individuals had prior or current experience delivering OEND programming in community-based settings, and people with lived and living substance use experience were represented in each of the expert categories. Findings from this initiative were summarized into a best practices implementation guide (Appendix A).

#### Organize and Mobilize for Implementation Effectiveness (OMIE)

Table 1 defines and specifies the 8 discrete implementation strategies that comprised OMIE. The OMIE approach was based on the Implementation and Sustainment Facilitation (ISF) Strategy, which is grounded in the theory of implementation effectiveness [27], and added discrete strategies from the Addiction Technology Transfer Center (ATTC), which were considered necessary elements from the original trial. Both ISF and ATTC have been described extensively elsewhere [44, 45]. Overall, our multi-component approach used external facilitation as the overarching strategy, by which seven other strategies were leveraged to support SSP staff and leadership. In total, 4 out of 7 discrete strategies from ISF were combined with 4 out of 10 discrete strategies from ATTC, detailed in Table 1. In addition to external facilitation, our multi-faceted OMIE approach included: organize implementation team meetings, identify and prepare champions, develop and organize quality monitoring system, assess for readiness and identify barriers, distribute educational materials and resources, conduct educational meetings, and provide ongoing consultation. The study team, comprised of people who had delivered SSP-based OEND services in the past year, researchers with over 20 years of SSP and OEND research experience, and national OEND implementation experts, collaboratively decided upon the discrete strategies for the OMIE approach. Decisions were grounded in shared understanding and discussion of implementation barriers SSPs faced generally and with OEND specifically.

**Table 1. Specification of Organize and Mobilize for Implementation Effectiveness**

Discrete strategy	Definition, actor, action, action target and temporality specification
1. External Facilitation	
Definition: provision of guidance, resources and coaching from an implementation expert who is external to the organization.
 
Actor: individual with previous OEND implementation experience within SSP settings.
 
Action: overarching mechanism by which the below strategies were delivered to SSP staff.
 
Action Target: SSP staff, including naloxone implementation team and leadership.
 
Temporality: Begins within 1 month of enrolling into the trial, occurs up to monthly for twelve months.

2. Organize implementation team meetings	
Definition: develop and support implementation team who are implementing OEND, giving them protected time to focus on implementation efforts, share experiences and support one another.
 
Actor: external implementation advisor (see above).
 
Action: web-based meetings with direct interaction between external implementation advisor and SSP staff.
 
Action Target: SSP staff, including naloxone implementation team and leadership.

	
Temporality: Begins within 1 month of enrolling into the trial, occurs up to monthly for twelve months.

3. Identify and prepare champions	
Definition: cultivate relationships with people who will champion and generate excitement within the organization regarding OEND best practice implementation.
 
Actor: external implementation advisor (see above).
 
Action: focused relationship building with SSP staff who are OEND implementation champion(s).
 
Action Target: SSP staff, including OEND implementation team and leadership.
 
Temporality: Begins with first organizational team meeting and continues as needed for 12 months

4. Develop and organize quality monitoring system	
Definition: develop and introduce an electronic tool that can be used to assess and prioritize best practice implementation efforts.
 
Actor: external implementation advisor (see above).
 
Action: using the electronic tool, external implementation advisor works with SSP staff to assess OEND best practice implementation and prioritize areas for focused efforts.
 
Action Target: SSP staff, including OEND implementation team and leadership.
 
Temporality: begins with first organizational team meeting and continues up to monthly for 12 months

5. Assess for readiness and identify barriers	
Definition: assess SSPs to determine degree of readiness for best practice implementation, and barriers that may impede implementation.
 
Actor: external implementation advisor (see above).
 
Action: focused conversation to discuss activities required for best practice implementation, readiness to carry out those activities and potential barriers that could impede those efforts.
 
Action Target: SSP staff, including OEND implementation team and leadership
 
Temporality: begins within 1 month of enrolling into the trial, occurs up to monthly for twelve months

6. Distribute educational materials and resources	
Definition: distribute educational materials (manuals, online trainings, etc.) electronically with regards to OEND best practices
 
Actor: external implementation advisor (see above).
 
Action: electronically distribute OEND best practices manual and other resources including implementation manuals and online trainings
 
Action Target: SSP staff, including OEND implementation team and leadership
 
Temporality: begins with first organizational team meeting and continues as needed for 12 months

7. Conduct educational meetings	
Definition: conduct educational sessions for providers and leadership with regards to OEND best practices
 
Actor: external implementation advisor (see above).
 
Action: web-based trainings with direct interaction between external implementation advisor and SSP staff.
 
Action Target: SSP staff, including OEND implementation team and leadership
 
Temporality: begins with first organizational team meeting and continues as needed for 12 months.

8. Provide ongoing consultation	
Definition: provide implementers with continued consultation with regards to OEND best practices.
 
Actor: external implementation advisor (see above).
 
Action: web-based meetings with direct interaction between external implementation advisor and SSP staff.
 
Action Target: SSP staff, including OEND implementation team and leadership
 
Temporality: begins within 1 month of enrolling into the trial, occurs via web-based meetings up to monthly for twelve months and as needed via electronic communication

SSP staff and organizational leadership in the OMIE arm were provided the opportunity to participate in 60-minute sessions once a month for up to 12 months. In addition to monthly sessions, facilitators were provided up to 2 hours to prepare for sessions and to identify and distribute resources to SSPs based on identified priorities. All sessions were offered virtually over audio-visual connections. Thus, the maximum possible dose for each SSP was 12 sessions or 36 hours. To maximize the extent to which the approach was implemented with consistency and quality, the project's lead and the study coordinator trained each facilitator, reviewed randomly selected facilitation session recordings, and held group supervisory meetings weekly to discuss successes, lessons learned, and emerging issues.

#### Data Collection

We carried out an interview-administered survey at SSPs baseline visit and at their 12-month follow-up after all facilitation-based activities had occurred. SSPs were paid a \$50 incentive for their time (~30 minutes) completing the baseline and the 12-month follow-up survey. In addition, the study coordinator tracked the number of sessions and the number of hours between external facilitators and SSP teams as part of a log of implementation activities. Follow-up to complete the 12-month follow-up survey ended in February 2022, marking the end of the trial approximately 12 months after the last SSP was enrolled.

#### Trial Outcomes

Our primary outcomes center on the multidimensional variable of implementation effectiveness (i.e., the consistency and quality of OEND implementation by SSP staff). Implementation effectiveness fit our broad objectives, by focusing on the extent to which our multifaceted, facilitation-based approach impacted OEND delivery at the organizational level. Accordingly, SSPs represent the primary unit of analysis. Proctor et al.'s taxonomy of implementation outcomes informs our operationalization of implementation effectiveness, focusing on the reach of SSPs' naloxone distribution (i.e., consistency) and fidelity to OEND best practices (i.e., quality)[46]. As such, the primary outcomes were the number of naloxone doses distributed in the past 3 months; the number of SSP participants receiving naloxone in the past 3 months, and the number of OEND best practices implemented. Importantly, prior research has shown that larger scale naloxone distribution has led to reductions in opioid overdose mortality, further supporting use of these measures as trial outcomes [17, 47, 48].

#### Covariates

The baseline survey also collected information on region of operation, the number of staff and volunteers at the SSP, staff training in OEND, the prior year's annual budget in dollars, the number of participant contacts at the SSP in the past 3 months.

#### Masking

Masking the SSP organizations and their staff to the assigned implementation strategy condition was not possible. Aside from the external facilitators who delivered the implementation strategies, research staff were blinded to all condition assignments, including the statistician throughout all analyses.

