#### Statistical Analysis Plan

Statistical analyses were conducted using an intent-to-treat approach. Descriptive statistics were used to summarize continuous outcomes and covariates by experimental condition; frequencies and percentages were used to summarize categorical measures. Given the varying sizes of SSPs, counts of naloxone doses and individuals receiving naloxone were summarized as a rate per number of participant contacts for syringe services in the past 3 months.

Negative binomial regression models were used to compare the number of naloxone doses distributed and contacts for naloxone refills or trainings by condition; the number of contacts for syringe services in the past 3 months was included as an offset. The model for naloxone doses was adjusted for baseline rate given the difference between conditions at baseline. The mean number of best practices adopted were compared by condition using a two-sample t-test. We also carried out a per-protocol dose response analyses, where OMIE SSPs were dichotomized at the median for the number of OMIE sessions (<10 sessions; 10+ sessions) and number of OMIE hours received (<12 hours; 12+ hours) and compared to Control SSPs. P-values <0.05 were considered statistically significant a priori. All analyses were conducted using Stata 16.1 (StataCorp LLC, Texas USA).

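### The masking statement exempts only the facilitators, but the plan's own procedures unblind the study coordinator, partly unblind the project lead, and reveal the arms in the dose-response analysis

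*Combined protocol and SAP*

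**What the plan says.** The Masking section makes two statements. For the programs: "Masking the SSP organizations and their staff to the assigned implementation strategy condition was not possible". For the research team: "Aside from the external facilitators who delivered the implementation strategies, research staff were blinded to all condition assignments, including the statistician throughout all analyses". The facilitators are the only exception among research staff, and the statistician's blinding is said to cover every analysis.

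Three other places bear on this:

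- **OMIE section, paragraph after Table 1.** It says that "the project's lead and the study coordinator trained each facilitator, reviewed randomly selected facilitation session recordings, and held group supervisory meetings weekly".
- **Data Collection.** It says that "the study coordinator tracked the number of sessions and the number of hours between external facilitators and SSP teams". The same section has the outcome survey administered by interview at baseline and at 12 months, without naming the interviewer.
- **Statistical Analysis Plan.** In the dose-response analysis, "OMIE SSPs were dichotomized at the median for the number of OMIE sessions" and likewise for hours, and the resulting groups are compared with Control.

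The recruitment section states that Control programs received only the disseminated recommendations. It also states that randomization followed the baseline survey.

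**The concern.** The programs and their staff know their arm, and they are also the survey respondents. Interviewer and analyst blinding are therefore the main masking safeguards left, and the document claims both in one broad sentence. If that sentence is wrong for some roles, a reader needs to know which roles, and whether they touched the outcome data or the primary analysis.

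Two features give this practical weight.

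- **Assessment.** One primary outcome is the number of best practices implemented. In Table 1 (the quality monitoring strategy), the facilitator uses an electronic tool with OMIE staff to assess and prioritize the same practices. An interviewer who had sat in supervision would have heard about that progress and could probe or score accordingly. Only the 12-month interview is exposed, because the baseline interview preceded allocation.
- **Analysis.** The model for naloxone doses was adjusted for the baseline rate because the arms differed at baseline, and no such adjustment is described for the other two outcomes. A choice that follows from observed data is easier to defend if the analyst could not tell the arms apart when making it.

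**Working it through.** No figure in the plan bears on masking, so the check is a comparison of the sections, role by role.

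**Study coordinator.** Only OMIE programs have facilitation sessions. A log of sessions and hours therefore identifies as OMIE every program with an entry. The coordinator also trained the facilitators, reviewed recordings and held weekly supervision. Masking does not exempt this role, so the sections contradict each other. One limit applies: an OMIE program that took up no sessions would not be told from Control by the log alone.

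**Project lead.** The lead shared the training, recording review and supervision, but is not said to have kept the log. Recordings were selected at random and supervision was in groups. The lead therefore learned the arm of the programs heard or discussed, which need not be all of them. The contradiction holds for those programs.

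**Statistician, dose-response analysis.** Suppose the arms carried neutral codes. Only one arm has session and hour counts, so attaching them identifies it. Suppose instead that a third party supplied only a coded three-level group. Under an equal split, an assumption because the plan uses simple randomization and gives no arm sizes, 105 programs give 105 / 2 = 52.5 per arm. A median split of one arm then gives two groups of about 52.5 / 2 = 26 beside one of about 52. Group size, or a cross-tabulation against the two-level code, shows which arm was divided. Blinding cannot hold for this analysis.

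**Statistician, primary comparisons.** The dose-response analysis is presented as an additional one. The plan does not state the order of the analyses, whether codes were used, or when the session data were merged. Blinding here is neither contradicted nor secured.

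**12-month interviewer.** The recruitment section says only that study staff gave the baseline survey. No section names who gave the 12-month survey, or keeps that person away from the log, recordings or supervision. Blinding here is also neither contradicted nor secured. The plan does not say who opened the allocation envelopes either.

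**Illustration only.** The documents give no basis for a size of bias. As an assumption, let unblinded interviewing shift the average best-practice count in the whole OMIE arm by δ standard deviations, with 52.5 programs per arm and no true effect. The non-centrality is δ / √(2/52.5) = δ / 0.195. The normal approximation to the two-sided t-test at 1.96 then gives:

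| Assumed δ | Non-centrality | Rejection rate |
|---|---|---|
| 0 | 0 | 5% |
| 0.1 | 0.51 | about 8.1% |
| 0.2 | 1.02 | about 17.6% |

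The first row applies if the interviewers were separate and blinded. The other rows need the shift to hold on average across the whole arm. The table does not cover the two negative binomial outcomes.

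**The case against.** The strongest reply is that only the wording of one sentence fails. Separate, blinded interviewers fit every section of the document, and primary comparisons run on coded arms before the session data arrived fit too. On that account the blinding that matters was intact. Two of the three primary outcomes are numerical counts, which leave less room for interviewer judgement. Respondents knew their arm whoever asked the questions, so a blinded interviewer would have removed only part of the risk. Follow-up ended in February 2022, so conduct can no longer be changed.

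Most of this stands. A reader might infer from the contradiction that outcome assessment was unblinded. The documents do not support that, because they never say who did the 12-month interviews. A reader might also infer that the statistician knew the arms during the primary comparisons. The order of analyses is not given, so that is not supported either. Nor do the documents show that the lead knew the full allocation, or that any bias favoured OMIE.

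The reply does not rescue the statement itself. It exempts one group where the procedures require more, and it covers an analysis that cannot be blinded. Since its account of the coordinator is wrong, it cannot be relied on for the interviewer or the primary analysis without further detail.

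**Conclusion.** The masking statement is contradicted in three respects: for the study coordinator, for the project lead as regards the programs heard or discussed, and for the statistician in the dose-response analysis. This follows from the text and rests on one premise, which the plan states: only OMIE programs received facilitation.

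Blinded 12-month assessment and blinded primary comparisons are not shown to have failed, but the plan does not secure them. The effect on the results is unknown and could be nil. The rejection rates above rest on an assumed shift, should not be cited as an estimate, and play no part in this conclusion. The point should be corrected before the blinding claim is repeated in a report. Confidence is high for the contradiction and does not extend to any actual bias.

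**What to change.** 1. **Correct the Masking section.** List the facilitators, the study coordinator and the project lead as unblinded, with the extent for each. Limit the statistician's blinding to the primary comparisons, if that is what happened.
2. **Account for the 12-month interviews.** As a design rule, the survey should be given by existing staff with no access to the session log, recordings or supervision meetings. Follow-up has ended, so report who did the interviews and what they had access to. If interviewer identity was recorded, repeat the primary comparisons without the programs interviewed by unblinded staff. If it was not recorded, say so.
3. **Account for the order of analysis.** As a design rule, the three primary comparisons should be completed and locked on coded arms before the session and hours log is merged. Report whether this was done, and label the dose-response analysis unblinded.

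The cost is a few sentences and at most one sensitivity analysis, with no extra staff. The downside is a less favourable blinding statement. The sensitivity analysis would also use fewer programs and so be less precise.

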#### Targeted Sample Size

The targeted sample size was estimated using PASS software [49]. We estimated that a sample of 100 SSPs (50 per arm) would provide 80% statistical power to detect a statistically significant ( $p<0.05$ ) medium effect size (Cohen's  $d = 0.45$ )[50] between study arms, assuming an

alpha of 0.05, standard deviation of 1.0 and two repeated measurements (baseline and 12-month follow-up) with a first-order autoregressive covariance structure and a correlation between observations on the same SSP of 0.3.

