### Recruitment, Eligibility, and Enrollment

To be eligible, an organization must have: 1) met the definition of an SSP – a program which primary function is to engage people who use drugs and provide them free drug use supplies to reduce harms associated with drug use, 2) implemented OEND for a minimum of 6 months, and 3) completed the NSSSP fielded from February to July 2019. We excluded organizations such as fire departments or emergency departments of hospitals that offered drug use supply distribution since it would be an ancillary function of these organizations and OEND programs that were not part of a SSP.

A total of 243 SSPs participated in the survey and were determined to be eligible. SSPs were organized into a randomized list and were contacted sequentially for recruitment into the trial. We recruited SSPs from September 2019 to February 2021. Within that timeframe, we paused recruitment activities from March to July 2020 due to the onset of the COVID-19 pandemic. The pause in recruitment activities primarily provided an opportunity for SSPs to adapt to COVID-19 changes, particularly for their adjustment to stay-at-home orders and adoption of delivery models that minimized close person-to-person contact.

To recruit SSPs, our study team initially contacted people in leadership role(s) at each SSP via email to set up a call to explain the study and carry out enrollment activities for organizations that were interested. Organizational leadership included executive directors, program managers, and/or site coordinators. For organizations interested in participating in the trial, study staff would obtain electronic/written informed consent from the organization to join the study, carry out the organizational agreement for participation, and administer the baseline survey. Following the baseline survey, SSPs were randomized using simple randomization to two study arms: 1) dissemination of OEND best practice recommendations (i.e., Control SSPs), or 2) the Organize and Mobilize for Implementation Effectiveness (OMIE) approach along with dissemination of the OEND best practice recommendations (i.e., OMIE SSPs). Sequentially numbered sealed envelopes were used to implement the random allocation sequence, which were concealed until the point of randomization.

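### The stated 80% power at d = 0.45 does not hold for the best-practices t-test (about 61% on 12-month values) and cannot be carried over to the negative binomial outcomes

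*Combined protocol and SAP*

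**What the plan says.** The Targeted Sample Size section gives one power statement for the trial: "a sample of 100 SSPs (50 per arm) would provide 80% statistical power". The effect is Cohen's d = 0.45 with standard deviation 1.0 and alpha 0.05. The design assumption is "two repeated measurements (baseline and 12-month follow-up) with a first-order autoregressive covariance structure", with a within-SSP correlation of 0.3. The section cites the PASS software but names no procedure, outcome or test.

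Trial Outcomes lists three primary outcomes: naloxone doses, participants receiving naloxone, "and the number of OEND best practices implemented". The Statistical Analysis Plan treats them as follows:

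- Best practices: "The mean number of best practices adopted were compared by condition using a two-sample t-test". No baseline term, time point or sidedness is given.
- Counts: "Negative binomial regression models were used to compare the number of naloxone doses distributed and contacts for naloxone refills or trainings by condition", with syringe-service contacts as an offset. Baseline adjustment is stated for the dose model only.
- Threshold: "P-values <0.05 were considered statistically significant a priori".

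On timing, Recruitment, Eligibility, and Enrollment says: "Following the baseline survey, SSPs were randomized using simple randomization to two study arms". Data Collection says: "We carried out an interview-administered survey at SSPs baseline visit and at their 12-month follow-up". There is therefore one measurement before randomization and one after.

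**The concern.** The power calculation and the analysis plan describe different analyses. The calculation gains precision from a second measurement per SSP; the best-practices t-test, as written, does not use one. The second measurement is also the baseline, taken before allocation, so it can help only as an adjustment variable and not as a second observation of the treatment effect.

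The consequence is confined to interpretation. A reader who relies on the stated 80% will think that a true effect of d = 0.45 had a 20% chance of being missed. If the real chance is about twice that, a non-significant result on best practices is much weaker evidence against a medium effect than the document suggests. For the two count outcomes the reader has no power basis at all, although the single statement looks as if it covers all three.

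**Working it through.** **Inputs** (all from Targeted Sample Size unless noted): 50 SSPs per arm, d = 0.45, SD 1.0, alpha 0.05, two measurements, correlation 0.3. With two time points, a first-order autoregressive structure is simply one correlation of 0.3. Two-sided testing is assumed; it is the version that reproduces the stated figure.

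**Formula.** With v the variance of the per-SSP quantity being compared,

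n per arm = 2 × (1.960 + 0.842)² × v / 0.45².

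Power at 50 per arm is taken from the noncentral t distribution with 98 degrees of freedom and noncentrality 0.45 / √(2v/50).

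**Step 1: reproduce the plan's figure.** Averaging the two visits gives v = (1 + 0.3)/2 = 0.65. Then n = 50.4 per arm, in line with the stated 50. Power at 50 per arm is 78.9% (t) or 79.7% (normal approximation). The one-sided version gives 87.0% (t) and does not match.

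**Step 2: what that reading requires.** It needs a difference of 0.45 averaged over both visits. Baseline comes before randomization, so its expected difference is 0. If the arms differ by 0.45 at 12 months only, the averaged difference is (0 + 0.45)/2 = 0.225, and the averaged test has about 28% power.

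**Step 3: the planned t-test.** One 12-month value per SSP gives v = 1 and noncentrality 0.45 / √(2/50) = 2.25. Power is 60.6% (61.4% by the normal approximation).

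**Step 4: other readings of a 12-month effect, 50 per arm.**

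| Analysis | v | Two-sided power | One-sided power |
|---|---|---|---|
| t-test, 12-month values | 1 | 60.6% | 72.2% |
| t-test, change from baseline | 2(1 − 0.3) = 1.4 | 46.9% | 59.6% |
| ANCOVA on baseline | 1 − 0.3² = 0.91 | 64.6% | 75.7% |

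None reaches 80%. A simulation of 100,000 trials at correlation 0.3 agrees: 60.8% for the two-sided 12-month t-test and 46.8% for the two-sided change score.

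**Step 5: what 80% would take.** For the two-sided 12-month t-test, the formula gives n = 77.5 per arm; the noncentral t gives 79 per arm (power 80.3%). With 50 per arm, the effect detectable with 80% power is d = 0.566.

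**Step 6: the enrolled number.** The Study Objective gives 105 SSPs. Assuming a 52/53 split and no dropout (the documents give no arm sizes), power is 62.7%.

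**Step 7: meaning for a null result.** With SD 1 and 50 per arm, the 95% confidence interval half-width is 1.984 × √(2/50) = 0.397. The interval excludes 0.45 only if the observed difference is below 0.45 − 0.397 = 0.053 SD.

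**Step 8: count outcomes.** A standardized difference with SD 1.0 does not convert to a rate ratio without a rate and a dispersion. The documents give none of the three, so no power figure can be derived, whether above or below 80%.

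**The case against.** The strongest reply is that nothing was miscalculated. The 80% reproduces under a recognized repeated-measures formula, and the sample size section never says that it refers to the best-practices t-test. That is right as far as it goes: this is a mismatch between power model and analysis, not a slip in arithmetic. But it is the only power statement for three primary outcomes, so a reader will apply it to them, and it matches no analysis in the plan.

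Second, the 61% rests on a time point and sidedness that the plan does not state, and the averaging explanation is a reconstruction, since the PASS procedure is not named. Both points stand as caveats. They do not change the direction: every alternative for a 12-month effect stays below 80%, and the power of a t-test with these inputs does not depend on which PASS procedure was used. They do mean that any correction should be conditional on the authors confirming those two details.

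Third, for the negative binomial outcomes the documents lack inputs; no figure is shown to be wrong. Agreed. The supportable statement is that power was not established for them, not that it was low.

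Fourth, the trial is complete, and confidence intervals now carry the interpretation. This limits the consequence, and the 0.05 SD threshold will shift with the observed SD and numbers analyzed. It does not remove the reason to correct a power figure that the document still states.

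**Conclusion.** The concern holds. On the section's own inputs, the two-sample t-test on best practices has about 61% power for d = 0.45 with 50 SSPs per arm, not 80%. The chance of missing that effect is about 39%, not 20%. This assumes a two-sided test on 12-month values, SD 1.0 and no dropout; the sample size section makes no allowance for dropout, and any loss would lower the figure. Under the other readings, two-sided power runs from 47% (change score) to 65% (ANCOVA), and the most favorable combination, one-sided ANCOVA, reaches 76%. The 80% cannot be carried over to the two negative binomial outcomes, for which no figure can be computed from the documents. Type I error and effect estimates are not affected.

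**What to change.** Leave the existing sample size text in place, as the record of what was planned, and add a labelled correction beside it. Subject to the authors confirming that the test is two-sided and uses 12-month values, it could read:

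> Correction: with 50 SSPs per arm, the two-sided two-sample t-test on 12-month best practices has about 61% power for d = 0.45; 80% power corresponds to d of about 0.57. The 80% figure does not carry over to the negative binomial outcomes, for which power was not established.

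Name the PASS procedure used. In the Statistical Analysis Plan, add one clause giving the time point and sidedness of the t-test; if they differ from the above, replace the 61% and 0.57 with the figures for the test actually used. Interpret non-significant results from the confidence intervals, with the corrected figures as context, and not against 80% power.

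The cost is a short note and one clause. It needs no further SSPs, no new data and no change to any analysis. The only downside is a less favorable stated power.
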